11.4 Measurement of Treatment/Intervention Effect

11.4.1 Target Lesions & Target Lymph Nodes

Measurable lesions (as defined in Section 11.2.1) up to a maximum of 5 lesions representative of all involved organs, should be identified as "Target Lesions" and recorded and measured at baseline. These lesions can be non-nodal or nodal (as defined in Section 11.2.1), where no more than 2 lesions are from the same organ and no more than 2 malignant nodal lesions are selected.

Note: If fewer than 5 target lesions and target lymph nodes are identified (as there often will be), there is no reason to perform additional studies beyond those specified in the protocol to discover new lesions.

- Target lesions and target lymph nodes should be selected on the basis of their size, be
 representative of all involved sites of disease, but in addition should be those that lend
 themselves to reproducible repeated measurements. It may be the case that, on occasion,
 the largest lesion (or malignant lymph node) does not lend itself to reproducible
 measurements in which circumstance the next largest lesion (or malignant lymph node)
 which can be measured reproducibly should be selected.
- Baseline Sum of Dimensions (BSD): A sum of the longest diameter for all target lesions plus the sum of the short axis of all the target lymph nodes will be calculated and reported as the baseline sum of dimensions (BSD). The BSD will be used as reference to further characterize any objective tumor response in the measurable dimension of the disease.
- Post-Baseline Sum of the Dimensions (PBSD): A sum of the longest diameter for all target lesions plus the sum of the short axis of all the target lymph nodes will be calculated and reported as the post-baseline sum of dimensions (PBSD). If the radiologist is able to provide an actual measure for the target lesion (or target lymph node), that should be recorded, even if it is below 0.5 cm. If the target lesion (or target lymph node) is believed to be present and is faintly seen but too small to measure, a default value of 0.5 cm should be assigned. If it is the opinion of the radiologist that the target lesion or target lymph node has likely disappeared, the measurement should be recorded as 0 cm.
- The minimum sum of the dimensions (MSD) is the minimum of the BSD and the PBSD.

11.4.2 Non-Target Lesions & Non-Target Lymph Nodes

Non-measurable sites of disease (Section 11.2.2) are classified as non-target lesions or non-target lymph nodes and should also be recorded at baseline. These lesions and lymph nodes should be followed in accord with 11.4.3.3.

11.4.3 Response Criteria

11.4.3.1 All target lesions and target lymph nodes followed by CT/MRI/PET-CT/Chest X-ray/physical examination must be measured on re-evaluation at evaluation times specified in Section 11.1. Specifically, a change in objective status to either a PR or CR cannot be done without re-measuring target lesions and target lymph nodes.

Note: Non-target lesions and non-target lymph nodes should be evaluated at each assessment, especially in the case of first response or confirmation of response. In selected circumstances, certain non-target organs may be evaluated less frequently. For example, bone scans may need to be repeated only when complete response is identified in target disease or when progression in bone is suspected.

11.4.3.2 Evaluation of Target Lesions

- **Complete Response (CR):** All of the following must be true:
 - a. Disappearance of all target lesions.
 - b. Each target lymph node must have reduction in short axis to < 1.0 cm.
- Partial Response (PR): At least a 30% decrease in PBSD (sum of the longest diameter for all target lesions plus the sum of the short axis of all the target lymph nodes at current evaluation) taking as reference the BSD (see Section 11.4.1).
- **Progression (PD):** At least one of the following must be true:
 - a. At least one new malignant lesion, which also includes any lymph node that was normal at baseline (< 1.0 cm short axis) and increased to ≥ 1.0 cm short axis during follow-up.
 - b. At least a 20% increase in PBSD (sum of the longest diameter for all target lesions plus the sum of the short axis of all the target lymph nodes at current evaluation) taking as reference the MSD (Section 11.4.1). In addition, the PBSD must also demonstrate an absolute increase of at least 0.5 cm from the MSD
 - c. See Section 11.3.2 for details in regards to the requirements for PD via FDG-PET imaging.
- **Stable Disease (SD):** Neither sufficient shrinkage to qualify for PR, nor sufficient increase to qualify for PD taking as reference the MSD.

11.4.3.3 Evaluation of Non-Target Lesions & Non-target Lymph Nodes

- Complete Response (CR): All of the following must be true:
 - a. Disappearance of all non-target lesions.
 - b. Each non-target lymph node must have a reduction in short axis to <1.0 cm.
- **Non-CR/Non-PD:** Persistence of one or more non-target lesions or non-target lymph nodes.
- **Progression (PD):** At least one of the following must be true:

- a. At least one new malignant lesion, which also includes any lymph node that was normal at baseline (< 1.0 cm short axis) and increased to ≥ 1.0 cm short axis during follow-up.
- b. Unequivocal progression of existing non-target lesions and non-target lymph nodes. (NOTE: Unequivocal progression should not normally trump target lesion and target lymph node status. It must be representative of overall disease status change.)
- c. See Section 11.3.2 for details in regards to the requirements for PD via FDG-PET imaging.

11.4.4 Overall Objective Status

The overall objective status for an evaluation is determined by combining the patient's status on target lesions, target lymph nodes, non-target lesions, non-target lymph nodes, and new disease as defined in the following tables:

Target Lesions & Target Lymph Nodes	Non-Target Lesions & Non-Target Lymph Nodes	New Sites of Disease	Overall Objective Status
CR	CR	No	CR
CR	Non-CR/Non-PD	No	PR
PR	CR Non-CR/Non-PD	No	PR
CR/PR	Not All Evaluated*	No	PR**
SD	CR Non-CR/Non-PD Not All Evaluated*	No	SD
Not all Evaluated	CR Non-CR/Non-PD Not All Evaluated*	No	Not Evaluated (NE)
PD	Unequivocal PD CR Non-CR/Non-PD Not All Evaluated*	Yes or No	PD
CR/PR/SD/PD/Not all Evaluated	Unequivocal PD	Yes or No	PD
CR/PR/SD/PD/Not all Evaluated	CR Non-CR/Non-PD Not All Evaluated*	Yes	PD

^{*} See Section 11.4.3.1

11.4.5 Symptomatic Deterioration: Patients with global deterioration of health status requiring discontinuation of treatment without objective evidence of disease progression at that time, and not either related to study treatment or other medical conditions, should be reported as PD due to "symptomatic deterioration." Every effort should be made to document the objective progression even after discontinuation of treatment due to symptomatic deterioration.

11.5 Definitions of analysis variables

Formal definitions of variables used in analyses can be found in the Statistical Considerations section of the protocol.

12.0 END OF TREATMENT/INTERVENTION

12.1 **Duration of Treatment**

- **12.1.1 CR, PR, or SD:** Patients who are in CR, PR or SD will continue on therapy until disease progression, intolerable toxicity, or patient refusal. After treatment is discontinued, patients will be followed per the study calendar in Section 5.0.
- **12.1.2 Disease Progression:** After disease progression, patients should be followed for survival per the study calendar (Section 5.0). Patients will be followed for 3 years after ending treatment.
- **12.1.3 Discontinuation of study agent:** If the patient discontinues enzalutamide, patients should be followed for survival per the study calendar (Section 5.0).

12.2 Managing ineligible patients and registered patients who never receive protocol intervention

Definition of ineligible patient

A study participant who is registered to the trial but does not meet all of the eligibility criteria is deemed to be ineligible.

Follow-up for ineligible patients who continue with protocol treatment

Patients who are deemed ineligible after registering may continue protocol treatment, provided the treating physician, study chair, and executive officer agree there are no safety concerns if the patient continues protocol treatment. All scans, tests, and data submission are to continue as if the patient were eligible. Notification of the local IRB may be necessary per local IRB policies.

Follow-up for ineligible patients who discontinue protocol treatment

For patients who are deemed ineligible after registering to the trial, who start treatment, but then discontinue study treatment, the same data submission requirements are to be followed as for those patients who are eligible and who discontinue study treatment.

Follow-up for patients who are registered, but who never start study treatment

For all study participants who are registered to the trial but who never receive study intervention (regardless of eligibility), the follow-up requirements are specified below.

Baseline and off-treatment notice data submission required. See the Data Submission Schedule accompanying the All Forms Packet.

12.3 Extraordinary Medical Circumstances

If, at any time the constraints of this protocol are detrimental to the patient's health and/or the patient no longer wishes to continue protocol therapy, protocol therapy shall be discontinued. In this event:

- Document the reason(s) for discontinuation of therapy on data forms.
- Follow the patient for protocol endpoints as required by the Study Calendar.

13.0 STATISTICAL CONSIDERATIONS

13.1 Study Overview

This single arm Phase II trial will assess the best overall response (BOR; by RECIST v1.1) associated with enzalutamide in patients with AR-positive salivary cancers. Given that this will be one of the first prospective studies ever conducted for AR-positive salivary cancers, and there are currently no standard therapies known to be effective for this disease, we will adopt a BOR of 5% as the null hypothesis and BOR of 20% as the alternative hypothesis. In addition to response, this study will also evaluate the progression-free survival (PFS), overall survival (OS), adverse events, and will also try to identify molecular predictors of response by examining genomic and transcriptional elements of androgen receptor biology.

13.2 Primary Endpoint

The primary endpoint for this study is the best overall response rate (BOR; by RECIST v1.1) associated with enzalutamide in patients with AR-positive salivary cancers documented to occur any time during the first 8 cycles (32 weeks). Per RECIST 1.1, responses need to be confirmed (2 consecutive responses at least 4 weeks apart) to count as a response (see Section 11). All eligible patients who are registered and start treatment will be evaluable for response. A Simon's optimal two-stage design will be utilized. In order to detect a difference between an unacceptable BOR of 5% and a desirable BOR of 20% with one-sided type one error of 5% and a power of 90%, at least two responses need to be observed among the 21 patients enrolled in the first stage. If this is achieved, then the study will progress to the second stage in which an additional 20 patients will be accrued. At the end of the trial, at least 5 responses need to be observed among a total of 41 patients enrolled for the drug to be considered worthy of further investigation. The study will be temporarily closed for stage 1 analysis, if necessary (i.e only if 1 or fewer responses have been observed at the time we have 21 evaluable patients enrolled).

13.3 Secondary Endpoints

The following endpoints will be evaluated: progression-free survival, overall survival, and adverse events.

Progression-Free Survival: Progression-free survival (PFS) is defined as the time from study entry to the first of either disease progression or death from any cause, where disease progression will be determined based on RECIST 1.1 criteria. PFS will be estimated using the Kaplan-Meier method. The median PFS and 95% confidence interval will be reported.

Overall Survival (OS): OS is defined as the time from study entry to death from any cause. OS will be estimated using the Kaplan-Meier method. The median OS and 95% confidence interval will be reported.

Adverse events: The maximum grade for each type of adverse event will be summarized using CTCAE version 4.0. The frequency and percentage of grade 3+ adverse events will be summarized. We will also closely monitor adverse events throughout the study.

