For patients that are withdrawn from the study for reasons other than radiographic progression, staging scans are to be performed every 3 months (+/- 2 months) until disease progression, for a maximum of 15 months from time of registration. For all patients withdrawn from the study, survival information is required every 6 months until 3 years following registration. Please refer to the full protocol text for a complete description of the eligibility criteria and treatment plan.

Alliance A091404

Table of Contents

Section	Page
 1.0 BACKGROUND	7 7
1.4 Rationale for Correlative Science Study (A091404-ST1)	9 9

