4.7 Stratification (or Grouping) Factors-None

5.0 STUDY CALENDAR

The pre-study testing intervals are guidelines only. Laboratory and clinical parameters during treatment are to be followed using individual institutional guidelines and the best clinical judgment of the responsible physician. It is expected that patients on this study will be cared for by physicians experienced in the treatment and supportive care of patients on this trial. One cycle is 28 days.

- To be completed ≤ 14 DAYS before registration: All laboratory studies, with exception of serum or urine HCG.
- To be completed \leq 28 DAYS before registration: Scans of any type which is to be utilized for tumor measurement per protocol, history and physical, weight/height, vital signs.

	Prior to Registration*	Days 1 and 15 of cycle 1, then Day 1 of every cycle *	At PD, withdrawal, or removal**
Tests & Observations			
History and physical, weight, PS	X	X	X
Height	X	•	
Pulse, Blood Pressure	X	X	
Registration Fatigue/Uniscale Assessment (Ψ)	X		
Adverse Event Assessment (π)	X	X	X
Patient Medication Diary (1)		X	X
Laboratory Studies			
Complete Blood Count, Differential, Platelets	X	X	X
Serum Creatinine	X	X	X
Albumin, glucose	X	X	X
AST, ALT, Alk. Phos., Bili	X	X	X
Serum or Urine HCG	X(2)		
Hormone panel***		X	X
Staging			
Central Pathology review for eligibility (including AR testing)	X(3)		
Radiographic imaging	X(4)	A	X**
Correlative studies: For patien	ts who consent to	participate	
Archival Tissue	5		
Tumor tissue biopsy	5#		
Research Blood Sample	5		

- * Labs completed prior to registration may be used for day 1 of cycle 1 tests if obtained ≤ 14 days prior to treatment. For subsequent cycles, labs, tests and observations may be obtained +/- 3 days from day 15 cycle 1, and +/- 5 days from day 1 of cycle 2 and beyond. Scans may be obtained +/- 7 days from date due.
- ** Post treatment follow-up evaluations and blood tests are required 30 days (+/- 5 days) after the end of treatment. For patients that are withdrawn from the study for reasons other than radiographic progression, staging scans are to be performed every 3 months (+/- 2 months) until disease progression, for a maximum of 15 months from time of registration. For all patients

- withdrawn from the study, survival information is required every 6 months until 3 years following registration. See also Section 12.0.

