- *** The hormone panel includes total and free testosterone. The hormone panel will be drawn first after study registration but PRIOR to initiation of study drug, and then Day 1 of every even-numbered cycle starting with cycle 2 times 3 (D1C2, D1C4, D1C6, +/- 7 days), and then at off study (+/- 7 days).
- Ψ To be completed after registration and ≤ 21 days prior to treatment, see Section 1.5 and Appendix I.
- π Solicited AEs are to be collected starting at baseline until off treatment (See Section 9.1). Routine AEs are to be collected starting after registration. See Section 9.3 for expedited reporting of SAEs.
- # At baseline (after registration and prior to day 1 cycle 1 of study drug) and after progression (See Section 6.2 for further information).
- Medication diary should be completed by the patient throughout treatment, and should be collected by site staff at day 1 of every cycle starting with day 1 cycle 2. See Appendix II.
- For women of childbearing potential (see Section 3.3). Must be done ≤ 5 days prior to registration and ≤ 10 days prior to day 1 cycle 1.
- 3 See Sections 6.2.
- 4 Baseline scans can include either: 1) a CT, spiral CT, or MRI, or 2) an FDG-PET scan and diagnostic CT performed with both IV and oral contrast, with the CT acquired with 5 mm or less slice thickness (see Section 11.3.2). Supporting documentation is to be submitted, per Section 6.1.1.
- 5 For patients who consent to submitting archival tumor tissue and research blood samples for correlative tissue analyses and banking, these should be obtained and submitted within 30 days of registration.
- A Every 2 cycles for the first 8 cycles (beginning Day 1 Cycle 3) then every 3 cycles (beginning with Day 1 Cycle 9), until evidence of progression or relapse. Confirmatory scans should also be obtained at least 4 weeks following documentation of objective response (see Section 11.0). Response assessment should include assessment of all sites of disease and use the same imaging method as was used at baseline.

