11.0 MEASUREMENT OF EFFECT

Response and progression will be evaluated in this study using the new international criteria proposed by the revised Response Evaluation Criteria in Solid Tumors (RECIST) guidelines (version 1.1).²⁶ Changes in the largest diameter (unidimensional measurement) of the tumor lesions and the short axis measurements in the case of lymph nodes are used in the RECIST guideline.

11.1 Schedule of Evaluations:

For the purposes of this study, patients **should be reevaluated every 8** weeks for the first 8 cycles and every 12 weeks thereafter. In addition to a baseline scan, confirmatory scans should also be obtained at least 4 weeks following initial documentation of objective response.

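### Does Section 13.3 need a PFS censoring rule because off-treatment scans stop at 15 months while deaths are collected to 3 years?

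*Combined protocol and SAP*

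**What the plan says.** Section 13.3 starts the PFS clock at study entry and stops it at the "first of either disease progression or death from any cause, where disease progression will be determined based on RECIST 1.1 criteria". It is estimated by Kaplan-Meier, and the median with its 95% confidence interval is reported. There is no test, null value or event target. No censoring date is stated. Section 11.5 sends the reader to Section 13 ("Formal definitions of variables used in analyses can be found in the Statistical Considerations section of the protocol"), and no other section supplies one.

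Three follow-up clocks bear on PFS:

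- On treatment, footnote A of the Study Calendar (Section 5.0) has scans continue "until evidence of progression or relapse", with no time limit.
- After leaving treatment without radiographic progression, scans are due "every 3 months (+/- 2 months) until disease progression, for a maximum of 15 months from time of registration" (Section 5.0, footnote **).
- For vital status, the schema and the same footnote state: "For all patients withdrawn from the study, survival information is required every 6 months until 3 years following registration".

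Two passages use the word progression without requiring an objective finding. Under Section 11.4.5, symptomatic deterioration "should be reported as PD due to" that cause. Section 8.1.6 describes patients who need radiotherapy as removed for disease progression.

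**The concern.** Read literally, a patient who leaves treatment without progression and dies at month 36 has a PFS event 36 - 15 = 21 months after the last scheduled scan. The unscanned months then count as progression-free, and only for patients who left treatment. For such a patient who is still alive, the text gives no date at all. Censoring at last contact would add unobserved time and lengthen the upper confidence limit and the tail of the curve. That tail also enters the exploratory Cox models in Section 13.4.

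The two labels raise the opposite worry. If symptomatic deterioration or removal for radiotherapy were coded as a PFS event, PFS would come out shorter than under RECIST 1.1. The cross-references can look circular: Section 11.5 points to Section 13, Section 13.2 points back to Section 11, and Section 11.4.5 sits inside Section 11. At stake is whether the reported PFS interval depends on a choice made after the data are seen.

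**Working it through.** **1. What the plan's own figures depend on.** The plan states no PFS figure to reproduce. Its decision rule is the two-stage response design of Section 13.2: go on with at least 2 responses among 21, and succeed with at least 5 among 41. The probability of success is the sum over x >= 2 of P(X1 = x) · P(X2 >= 5 - x), with X1 ~ Bin(21, p) and X2 ~ Bin(20, p). At p = 0.05 it is 0.0457; at p = 0.20 it is 0.9017. This agrees with the stated 5% and 90%, and PFS enters nowhere.

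**2. How many patients the scan limit can reach.** With the accrual in Section 13.6, 6 + 15 × 2 = 36 of 45 patients are enrolled by study month 21, so 36 are past month 15 at the month-36 analysis (Section 13.10). That count includes patients who have progressed and patients still scanned on treatment. The full 21-month gap needs 36 months of follow-up. At month 36 only one patient has 35 months or more, and six have 30 or more. Section 12.1.2 counts the 3 years from the end of treatment instead of from registration, but neither clock can bind before this analysis.

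**3. Size of the scan-limit effect.** The documents do not give the inputs, so these are assumptions:

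- 41 patients, accrual as in Section 13.6, data cut at month 36;
- exponential PFS with median 12 months (the figure in Section 1.2 from a 10-patient series of another drug) or 5 months;
- 10, 20 or 30% leave treatment without radiographic progression;
- median 6 or 12 months from progression to death;
- off-treatment progression is seen only to month 15, or at removal if later;
- Kaplan-Meier with log-log limits, 3,000 simulated datasets per setting.

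At median 12, about 1.8 / 3.7 / 5.7 of 41 patients are progression-free past their last scan. The typical upper 95% limit of the median, in months, is:

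| Handling | 10% leave | 20% leave | 30% leave |
|---|---|---|---|
| Deaths at own date, living censored at last contact | 18.5 | 18.9-19.0 | 19.4-19.8 |
| Deaths at own date, living censored at last scan | 18.1-18.2 | 18.3-18.4 | 18.7 |
| As the row above, but deaths more than 5 months after the last scan censored in off-treatment patients past month 15 | 18.1-18.2 | 18.2-18.3 | 18.5 |

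Had scanning continued, the limit would be 18.1-18.3.

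First row minus second: from 18.5 - 18.2 = 0.3 to 19.8 - 18.7 = 1.1 months. This is the cost of censoring living patients at last contact, which Section 13.3 does not prescribe. Second row minus third: at most about 0.2 months, which is all that a late-death rule adds. Deaths more than 5 months after the last scan average only 0.15-0.74 patients per trial. At median 5, neither the median nor its limits change.

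**4. The two labels.** The passages side by side:

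- Section 13.3 ties progression to RECIST 1.1.
- Section 11.4.5 itself describes deterioration without objective progression, and asks that objective progression still be documented after treatment stops.
- Section 6.1.1 requires a radiology report upon progression.
- Footnote ** keeps these patients on scans, because they did not leave for radiographic progression.
- Section 8.1.6 gives a reason for leaving therapy; it is not an entry in the objective-status table of Section 11.4.4.
- The back-reference in Section 13.2 ("to count as a response (see Section 11") concerns confirmation of response, so the circle does not pass through PFS.

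Together these mean following labelled patients to objective progression or death. If the labels were nevertheless coded as events, the median would fall by 0.1-0.9 months (assuming 5-20% of patients labelled, 2-4 months before progression). It would fall by 0 to 12.9 - 10.1 = 2.8 months if label timing were unrelated to true progression. For comparison, an exponential 95% interval with 41 events is 3.8-7.0 around a median of 5 and 9.0-16.7 around 12.

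**The case for a change.** The strongest case for amending is that this is a single-arm, open study and one of the first prospective studies in this disease. Its PFS interval will be read closely, and event and censoring rules are best fixed before the data are seen. One added sentence would cost almost nothing. With last-contact censoring, the upper limit differs from that under the late-death rule in 13%, 23-24% and 31-34% of simulated datasets (10, 20 and 30% leaving, median 12). Even last-scan censoring leaves the limit 18.7 - 18.3 = 0.4 to 18.7 - 18.1 = 0.6 months longer than continued scanning at 30% leaving.

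The omission itself stands, and writing the date down would be tidy. What does not stand is that the plan as written leads to the longer limit. Most of that shift needs last-contact censoring, which is an assumption and not the usual practice for a scan-based endpoint. The late-death rule recovers only about 0.2 months. It also departs from the plan's explicit inclusion of death from any cause, and takes 24-month PFS slightly below its true 25% (23.9-24.5% at 30% leaving). Its 5-month allowance (3 + 2) is one reading of footnote **: if the two-month tolerance applies to each scheduled date, consecutive scans can be 3 + 2 + 2 = 7 months apart. It is at best a sensitivity analysis.

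**Conclusion.** No change is needed. Section 13.3 leaves out a detail that an analyst fills in the standard way: progression by RECIST 1.1, deaths from any cause as events, and everyone else censored at the last evaluable scan. On that reading the median is essentially unaffected. The choice between keeping and censoring late deaths is worth no more than about 0.2 months on the upper limit at median 12, and nothing at median 5. The labels in Sections 11.4.5 and 8.1.6 do not override the RECIST 1.1 wording, although the word progression is used loosely there.

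The sizes rest on assumed exponential PFS, 10-30% leaving treatment without radiographic progression, and assumed survival after progression; the documents give none of these. The conclusion would weaken if the analyst censored living patients at last contact (0.3-1.1 months on the upper limit at median 12) or coded the labels as events. Even then only a descriptive secondary endpoint and exploratory models are touched; the primary endpoint and the go/no-go rule are not.

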2.2 Secondary objective(s)

- 2.2.1 To evaluate the progression-free survival (PFS) of AR-positive salivary cancer patients treated with enzalutamide.
- 2.2.2 To evaluate the overall survival (OS) of AR-positive salivary cancer patients treated with enzalutamide.
- 2.2.3 To evaluate the safety/tolerability of enzalutamide for patients with AR-positive salivary cancer.

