9.1 Routine adverse event reporting

Adverse event data collection and reporting, which are required as part of every clinical trial are done to ensure the safety of patients enrolled in the studies as well as those who will enroll in future studies using similar agents. Adverse events are reported in a routine manner at scheduled times according to the study calendar in Section 5.0. For this trial, the Adverse Events: Solicited and Adverse Events: Other forms are used for routine AE reporting in Rave.

Solicited Adverse Events: The following adverse events are considered "expected" and their presence/absence should be solicited, and severity graded, at baseline and for each cycle of treatment. Please note that diarrhea will be graded at baseline based on recording number of stools per day.

CTCAE v4.0 Term	CTCAE v4.0 System Organ Class (SOC)
Fatigue	General disorders
Hot Flashes	Vascular disorders
Diarrhea	Gastrointestinal disorders
Hypertension	Vascular disorders
Dizziness	Nervous system disorders
Seizures	Nervous system disorders
Localized Edema	General disorders
Gynecomastia	Reproductive system and breast disorders
Breast pain	Reproductive system and breast disorders
Weight loss	Investigations

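### Section 13.3 states no use of the baseline grade for solicited adverse events, so an unchanged pre-treatment symptom counts at its full grade

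*Combined protocol and SAP*

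**What the plan says.** Section 13.3 gives two analysis rules for adverse events: "The maximum grade for each type of adverse event will be summarized using CTCAE version 4.0", and "The frequency and percentage of grade 3+ adverse events will be summarized". It adds a commitment to close monitoring. It defines no treatment-emergent event, sets no time window for the maximum, and mentions neither baseline grade nor attribution. No other section supplies a baseline rule.

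This summary serves secondary objective 2.2.3: "To evaluate the safety/tolerability of enzalutamide for patients with AR-positive salivary cancer". There is no comparator; Section 13.1 begins "This single arm Phase II trial will assess the best overall response".

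The baseline grades exist. For the ten solicited terms, Section 9.1 says that "their presence/absence should be solicited, and severity graded, at baseline and for each cycle of treatment". The Section 5.0 calendar notes agree: "Solicited AEs are to be collected starting at baseline until off treatment". For all other events, "Routine AEs are to be collected starting after registration". Diarrhea has its own baseline instruction in Section 9.1: "diarrhea will be graded at baseline based on recording number of stools per day".

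**The concern.** A maximum grade describes what happened on treatment only if patients start without the symptom, or if the starting grade is taken into account. The protocol's own text makes pre-existing solicited symptoms plausible. Sections 8.1.1 and 8.1.3 let a patient already on an LH-RH agonist or antagonist continue it, and Section 1.3 lists fatigue and hot flashes among the toxicities of androgen deprivation. Both are solicited terms. Section 3.3 also admits patients with metastatic disease, any number of prior treatment lines and ECOG status 1.

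At stake is the reading of objective 2.2.3. Section 1.3 justifies enzalutamide without castration partly on expected tolerability, naming fatigue and hot flashes. Those terms can be inflated in the planned table, in some patients by symptoms of continued androgen deprivation, and no control arm shows the background level.

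**Working it through.** **1. The plan's own figures.** The plan gives no adverse-event rate to reproduce. Its design figures (Section 13.2) do reproduce. With X1 ~ Bin(21, p) and X2 ~ Bin(20, p), the chance of declaring activity is the sum over x = 2,…,21 of P(X1 = x) · P(X2 ≥ max(0, 5 − x)). This gives 0.0457 at p = 0.05 and 0.9017 at p = 0.20, against the stated 5% and 90%. No adverse-event quantity enters, so this point does not alter them.

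**2. What the rule does to individual patients.**
- Fatigue grade 2 at baseline and grade 2 in every cycle: the maximum is 2, whether or not the baseline visit is included. The patient is listed with grade 2 fatigue. A new-or-worsened rule asks whether 2 > 2 and does not count the patient.
- Fatigue grade 2 at baseline and absent in every cycle: the maximum is 2 if the baseline visit is included and 0 if it is not. Section 13.3 does not say which applies.
- Fatigue grade 1 at baseline, rising to grade 2: counted at grade 2 under both rules.

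The two rules therefore differ only for patients whose symptom is unchanged or improved.

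**3. Size for one solicited term, any grade.** Inputs:
- N = 41 (Section 13.5). Section 13.3 names no safety denominator.
- b = share with a baseline symptom that persists without worsening. Assumed 10–40%; the documents give no figure.
- w = share with a new or worsened symptom. Assumed 20% of all patients.

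By definition the two groups do not overlap, so planned table = b + w, baseline-adjusted table = w, and excess = b, or 41b patients.

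| b | Planned table | Adjusted table | Excess |
|---|---|---|---|
| 10% | 30% (12.3 of 41) | 20% (8.2) | 4.1 |
| 20% | 40% (16.4) | 20% (8.2) | 8.2 |
| 30% | 50% (20.5) | 20% (8.2) | 12.3 |
| 40% | 60% (24.6) | 20% (8.2) | 16.4 |

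The excess does not depend on w: with w = 0 the planned table would still show 10–40%.

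**4. Sensitivity.** Suppose instead that some patients with a baseline symptom also have a new or worsened event, independently of having it at baseline. The planned table then shows 1 − (1 − b)(1 − w): 1 − 0.90 × 0.80 = 28% at b = 10%, and 1 − 0.60 × 0.80 = 52% at b = 40%. The excess over 20% is 3.3 to 13.1 of 41. Direction and order of size are the same.

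**5. Grade 3 or higher.** If a share g has a given solicited term at grade 3 or higher at baseline and it persists, the chance that at least one of 41 patients is counted for it is 1 − (1 − g)^41. This is 34%, 56% and 88% for assumed g of 1%, 2% and 5%. The expected number of such patients is small: 0.4, 0.8 and 2.1.

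**The case against.** The strongest reply is that Section 13.3 is silent, not wrong: a brief descriptive plan, with the baseline grades in the database for the analyst to use. That is fair as to intent. A reader might infer that the plan chooses to discard the baseline grade, or to report baseline symptoms as toxicity. The documents say neither: the section speaks of adverse events and does not mention baseline. Followed as written, however, the rule still counts an unchanged symptom.

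A second reply is that investigators attribute every event (Section 9.0), and Section 9.2 filters low-grade unrelated events. Attribution is useful further information, but Section 13.3 does not use it; within Section 13 it appears only in the stopping rule of 13.8. The Section 9.2 filter applies in addition to the solicited terms, so it does not screen them.

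A third reply limits the scope, and it stands. Seizure history is an exclusion (3.3.7). Weight loss is a change measure, with weight recorded before registration. Diarrhea has a baseline stool count. ECOG 0–1 entry makes baseline grade 3 or higher symptoms less likely.

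A reader might also take the blood pressure limit in 3.3.7 to mean that raised pressure at entry is expected. It shows only that pressure up to that limit is permitted. The documents give neither its frequency nor the CTCAE thresholds needed to grade it.

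**Conclusion.** The point holds for solicited terms. Section 13.3 states no use of a baseline grade that the trial collects, and its maximum-grade rule, applied literally, counts persistent pre-treatment symptoms in full. Under the assumed 10–40% non-worsening baseline prevalence and a further 20% new or worsened, the planned table shows 30–60% instead of 20%, an excess of about 4 to 16 of 41 patients per term. These are illustrations; the prevalence has no anchor in the documents.

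The effect is mainly on lower grades and least relevant to seizure and weight loss. It would go too far to infer that all adverse-event counts are inflated: non-solicited events are collected only after registration. The stopping rule counts treatment-related deaths and seizures, so it is unaffected, as are the primary endpoint and sample size. This is a cheap improvement, not a flaw in the design.

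**What to change.** Add to Section 13.3: *For solicited adverse events, the maximum grade is taken over post-baseline assessments only. A table counting patients whose post-baseline maximum grade exceeds their baseline grade, by grade reached, is shown beside the unadjusted maximum-grade table, and grade 3+ frequencies for solicited terms are given both ways.*

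Non-solicited events have no baseline grade and stay as now planned. The change needs no new data, visits or patients. The cost is a slightly longer safety output: a second table for the solicited terms and a second grade 3+ column. Fixing the rule in advance also avoids choosing between summaries after the results are seen.
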